The O₂VERLAP study focuses on a subset of the Chronic Obstructive Pulmonary Disease (i.e. COPD) community that are also living with a diagnosis of Sleep Apnea (i.e. SA); having a diagnosis of both COPD and SA is referred to as Overlap Syndrome (i.e. OS). There are about 300 million people living with COPD globally; of those, OSA affects over 25% of older adults with rates increasing in association with the obesity epidemic. There are approximately 51-75 million individuals living with OS worldwide. This subset of the COPD community is met with increased morbidity and mortality rates compared to either diagnosis alone. The primary treatment for OSA is continuous positive airway pressure (i.e. CPAP, sometimes shortened to PAP). When individuals with OS are adherent to their nighttime CPAP therapies they see significantly improved outcomes, comparable to individuals living with a diagnosis of COPD alone. As a result, the primary aim of this study is to improve CPAP adherence in patients living with OS. The study hopes to do this through a proactive, peer-support based intervention, supplemented by an online curriculum and access to remote CPAP adherence monitoring data and feedback. Peer-coaches will include individuals who are living with COPD and OSA, who are similar to the study population. The COPD Information Line associates will act in this peer-support role through dyadic, telephone-based communication and through secure online chat. The COPD Information Line peer-coaches will be able to provide participants experience-based advice, patient-centered guidance on troubleshooting adherence barriers, as well as patient-centered advice on how to facilitate CPAP adherence. Peer-coaches will also include Respiratory Therapists who will be able to provide coaching from the perspective of a caregiver. Additionally, all peer-based support aims to provide emotional and social support to participants. The Participants will have the ability to chat with their peer coaches online, both in real-time and asynchronously, and will additionally have weekly check ins with their coaches. The curriculum addresses many common CPAP adherence barriers and facilitators. The literature suggests that the combination of peer-support and self-learning can cultivate patient activation and the use of self-management strategies. Ultimately, we expect that this will improve CPAP adherence rates and patient-centered outcomes at 6 weeks and 12 weeks.

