Aim #1: Improve adherence to PAP therapy at six weeks in proactive care arm.

Aim #2: Improve patient-centered outcomes (daytime functioning and sleep quality) at six and twelve weeks in proactive care arm.

Background

Chronic Obstructive Pulmonary Disease (COPD) is a group of progressive and debilitating respiratory conditions that affect 15-25 million Americans¹ and over 300 million people worldwide.² COPD is the third leading cause of death and the second leading cause of disability in the United States.³ Each year, COPD results in as many as 800,000 hospital admissions and 1.5 million emergency room visits. Obstructive Sleep Apnea (OSA) is a prevalent chronic medical condition characterized by repeated stops or near stops of breathing during sleep due to collapse of the tissues in the airway.⁴ These breathing episodes last 10 seconds or more, and cause repeated sleep disruptions and oxygen desaturations that lead to important health consequences. OSA affects 17% of adults and over 25% of older adults,⁵ with rates increasing in association with the obesity epidemic.⁶ Sleep apnea aggregates in families,⁷ affects all age groups, and disproportionately affects minorities⁸ and those from poor neighborhoods.⁹ Sleep apnea requires immediate and ongoing therapy because it lowers blood-oxygen levels and disrupts sleep, and is associated with hypertension, myocardial infarction, stroke, atrial

fibrillation, and early mortality and results in an increase of depression, anxiety, cognitive issues, erectile dysfunction, irritability, daytime sleepiness and motor vehicle crashes.¹⁰⁻¹⁷

Separately, COPD and OSA contribute to the morbidity and mortality of hundreds of thousands of Americans every year. However, when OSA coexists with COPD it is referred to as the Overlap Syndrome (OS).¹⁸ OSA is prevalent in at least 10-15% of patients diagnosed with COPD.¹⁹ While the prevalence rate of OSA is similar in patients with COPD as in the general population, individuals with both of these conditions but who do not use continuous positive airway pressure (CPAP) therapy at night during sleep, have an increased risk of death and more hospitalizations from acute exacerbations, demonstrating the importance of OSA treatment.²⁰

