have online access to adherence monitoring data to track their progress as they advance through the study program.

II. Criteria for Subject Selection

Number of subjects

The goal is to recruit 330 participants into the study to result in analyzable data of 300 participants (assumes ~10% attrition).

Gender of Subjects

There are no gender-based enrollment restrictions. Subjects of all genders will be recruited to enroll.

Age of Subjects

Subjects recruited for this study will be adults aged 40 and above.

Racial & Ethnic Origin

There are no enrollment restrictions based on race or ethnicity.

Inclusion Criteria

The inclusion criteria are as follows:

1. Age: ≥ 40 years
2. Primary language: English
3. Diagnosed with both Chronic Obstructive Pulmonary Disease (COPD) and Obstructive Sleep Apnea (OSA)
4. Prescription for positive airway pressure therapy (PAP). There should be no minimum or maximum flow required (i.e., no limitation on PAP modality).
5. Access to the internet via a PC, tablet, or smart phone to complete all study activities from home or remotely
6. PAP device with wireless modem

Exclusion Criteria

1. Non-English speakers
2. Life expectancy less than or equal to six months

Exclusion criteria includes non-English speakers and those whose life expectancy is less than or equal to six months. The study does not currently have the resources to translate the online curriculum into multiple languages, nor does it have the funds to recruit multi-lingual peer coaches. Additionally, as indicated in the inclusion criteria, access to a computer and internet are necessary for participants to complete the study activities.

Vulnerable Subjects

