As such, both Philips Respironics and Resmed have participated in the development of the data transfer workflow. Data will flow from the ResMed Airview system or Philips Respironics Encore Anywhere online system, through the necessary API's, managed by Corepoint Health integration engine, into the DatStat study platform. After providing the necessary information to either ResMed Inc. or Philips Respironics's data stewards, which is inclusive of proof of a participant's E-Consent, the participant Name, DOB and CPAP device serial number, the data steward will be required to provide the following data variables via the API workflow:

Weekly Updates on Critical Adherence Monitoring Data Variables

- 1) Total Time Connected (i.e. total time in minutes using a CPAP each evening)
- 2) Air Leakage (i.e. number of minutes the Sleep Apnea Mask is leaking air beyond a given threshold)
- 3) Apnea Hypopnea Index (i.e. a record of the number of apneas an individual is experiencing each evening).

These three variables are critical, quantitative indications, of an individual's adherence to CPAP therapy (i.e. the studies primary outcome) and may also provide insight on how to improve adherence. Monitoring these CPAP therapy variables will help both the research participants and authorized research staff to tailor a participant's goal-setting on a weekly basis, acknowledge progress and troubleshoot difficult weeks. The participants randomized to the proactive care arm will review and discuss their data on a weekly basis with a peer-coach to address these topics. Proactive care participants will also be encouraged to call their Peer-coaches during regular business hours via the C.O.P.D. Information Line and will also be encouraged to chat synchronously or asynchronously with Peer-coaches using the study portal.

Baseline Survey Package

All participants will be assigned a baseline survey package. Together the survey's measure a number of important patient-centered outcomes, like daytime sleepiness, daytime functioning, psychosocial factors influencing the survey's included are:

- 1) Functional Outcomes of Sleep Questionnaire (FOSQ)
- 2) COPD Assessment Test (CAT)
- 3) Epworth Sleepiness Scale (ESS)
- 4) Pittsburgh Sleep Quality Index (PSQI)
- 5) Patient Reported Outcomes Measures Information Systems Survey (PROMIS)

Randomization

A participant must have completed the following steps in order to move on to randomization.

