Patient ID, Email, Phone Number sent to Info Line via salesforce email	Coordinator	X							
Baseline Surveys	Coordinator and Participant	X							
30-days of Baseline CPAP Adherence Data uploaded to portal	Coordinator and ResMed or Philips (PC Arm Only)	X							
Self-report Oxygen Adherence Baseline	Coordinator and Participant (only participants prescribed O ₂)	X							
1st Call from Respiratory Therapist Coach; confirm participant can send and receive messages to RT Group; fill out PAP use survey and O ₂ use survey, if applicable.	RT Coach and Participant (ALL participants)		X						
1st Message from Peer Coach in portal; confirm participant can send and receive messages; fill out Journal, review and set goals. Fill out My Calendar, review.	Peer Coach (PC Arm Only)		X						
1st call from peer Coach and Module 1 completed together	Peer Coach and Participant (PC Arm Only)		X						
Module 2 Fundamentals of COPD	Participant (PC Arm Only)		X						
Module 3 Fundamentals of Sleep Apnea	Participant (PC Arm Only)			X					

Self-report Oxygen Adherence 30-days	Coordinator and Participant (only participants prescribed O ₂)				X			
6-week surveys +1 week (i.e. FOSQ, CAT, ESS, PSQI, PROMIS surveys)	Participant (PC Arm Only)			X				
Module 4 PAP in Depth I	Participant (PC Arm Only)			X				
Module 5 PAP in Depth II	Participant (PC Arm Only)				X			
Module 6 Oxygen in Depth	Participant (PC Arm Only)					X		
Module 7 Oxygen with your PAP device	Participant (PC Arm Only)						X	
Self-report Oxygen Adherence 12 weeks	Coordinator and Participant (only participants prescribed O ₂)							X
12-week (+1 week) follow-up surveys	Participant (PC Arm Only)							X
Peer Coach Calls	Peer Coach and Participant (PC Arm Only)	X	X	X	X	X	X	
RT Coach Calls	RT Coach and Participant (PC Arm Only)	X				X	X	
SAE and AE reporting	ALL study staff members	X	X	X	X	X	X	X
Exit Call from coordinator	Coordinator and Participant							X

Peer Coaches

Peer coaches will generally help with the following:

- 1) The management of a chronic illness
- 2) Health literacy
- 3) Emotional Support
- 4) Social Support
- 5) Experience-based feedback
- 6) Goal-setting

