Accessing the online curriculum, health monitoring data and peer coaching present minimal risk to study participants. Thus, the project was deemed to not need a data-safety monitoring board.

Overarching approach to analyses

Preliminary analyses will begin by examining the distribution of study variables and provide descriptive statistics (e.g., mean, median, standard deviation, quartiles for continuous variable, frequency and percentage for categorical variables) about the study population. Patient characteristics will be compared among study arms by a series of Kruskal-Wallis tests and Chi-square tests (or Fisher's exact tests as appropriate). Variables on which the groups differ initially will be explored as covariates in subsequent analyses. In case of missing data, appropriate data analytic techniques will be used, which may include deletion, imputation, inclusion of an indicator of missing values, or pattern-mixture modeling. The primary analysis will be as intent-to-treat (including all enrolled subjects) and all analyses will be performed using two- sided tests with alpha=0.05. Analyses will be conducted using SAS and R statistical software. Analysis plans to address each hypothesis are as follows:

Study Primary Aim

Our hypothesis is that CPAP adherence at the 6-week time point will be improved in the proactive care group compared to the reactive care group. Random effects model will be used to compare the mean CPAP adherence over 6 months between proactive and reactive care groups. A random intercept will be included in the model to account for the repeated measures of CPAP

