adherence over 6 months within each patient. Daily CPAP adherence data will be used for the analyses. Multivariable random effects model will be used to assess the difference in CPAP adherence between the proactive care and the reactive care group with adjustment for potential covariates. Adjustments will be made to correct for baseline imbalances across study groups and to adjust for variables known to influence the outcome. Baseline demographic and other clinically important characteristics will be assessed for imbalance among the study groups using Wilcoxon rank sum test, Chi-square or Fisher's exact test, and their association with the outcome using a simple random effects model. These variables will be included as covariates in the multivariable model if found moderately associated with the outcome or unbalanced ($p<0.15$) across groups. All covariates significant at $p<0.10$ will be kept in the final model. As a secondary analysis, we will fit a random effects model to assess the difference in CPAP adherence change between two groups. The random effects model is useful for examining longitudinal measures and it will include all available data. An interaction between time and intervention will be included in the model, both random intercept and random slope will be assessed, likelihood ratio test will be used for model comparison. Similarly, multivariable random effects model will be used to assess this association with adjustment for potential covariates.

Study Secondary Aims

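### Aim 1 and the primary hypothesis concern CPAP adherence at 6 weeks, but the primary model averages it over 6 months, a period scheduled nowhere else in the plan

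*Combined protocol and SAP*

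**What the plan says.** The aims at the start of the protocol give the primary objective as "Aim #1: Improve adherence to PAP therapy at six weeks in proactive care arm". The Study Primary Aim section, under Data Analysis and Data Monitoring, agrees: "Our hypothesis is that CPAP adherence at the 6-week time point will be improved in the proactive care group".

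The sentence that follows defines the primary analysis: "Random effects model will be used to compare the mean CPAP adherence over 6 months between proactive and reactive care groups". The next sentence adds a random intercept to handle repeated measures of "adherence over 6 months within each patient", and daily CPAP data are to be used. The 6-month period is therefore written twice, both times for the primary model.

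The same section then plans a secondary model of change in adherence with a time-by-intervention interaction. It names no contrast at 6 weeks.

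The study summary expects the programme to "improve CPAP adherence rates and patient-centered outcomes at 6 weeks and 12 weeks". The last survey in Table 1.0 is "12-week (+1 week) follow-up surveys".

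**The concern.** The objective and the analysis meant to test it name different periods, in adjacent sentences. The difference affects what is estimated. A 6-week objective asks what the intervention achieves by the end of six weeks, within the seven weeks in which weekly peer coaching is expected (Peer Coaches section). A mean over 6 months gives most of its weight to nights after that point, so it largely measures whether any effect lasts.

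The ambiguity also leaves a choice open on the primary endpoint. An analyst could defend 6 weeks or 6 months from the text, and could do so after seeing the data. The secondary interaction model does not close the gap, because it is not primary and does not say at which time the arms are compared.

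**Working it through.** The plan gives no figure for this point: no expected CPAP effect, standard deviation or power. The check is a comparison of the stated times, followed by arithmetic on the window.

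**Step 1. Times stated in the plan**

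| Item | Time | Where |
|---|---|---|
| Aim 1 | 6 weeks | Aims |
| Primary hypothesis | 6 weeks | Study Primary Aim |
| Primary model | 6 months (twice) | Study Primary Aim |
| Patient-centered outcomes, including long-term maintenance | 6 and 12 weeks | Study Secondary Aims |
| Surveys | 6 and 12 weeks, +1 week | Table 1.0 |
| Last column of activity table | weeks 8-15 | Table 1.0 |
| Oxygen self-report, last | 12 weeks or 90 days | Table 1.0; Appendix B |
| Payments after randomization | 6 and 12 weeks | Payment for Participation |
| Expected weekly coaching | first seven weeks | Peer Coaches |
| CPAP data feed | weekly, no stated end | Remote Adherence Monitoring Set-up Activities |

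Six months appears in two other places: the exclusion "Life expectancy less than or equal to six months", and a question on replacing equipment in the respiratory therapist script (Appendix C). Neither schedules follow-up.

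**Step 2. What the primary model estimates**

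The description gives a group comparison, a random intercept and daily data, with no time or group-by-time term. With complete nightly data, the group coefficient is the arm difference averaged over all nights in the window.

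Take 6 months as 26 weeks = 182 days, counted from randomization:

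- nights to week 6: 42/182 = 0.231
- nights after week 6: 140/182 = 0.769
- nights after week 7: (182 - 49)/182 = 133/182 = 0.731

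Hence: 6-month mean difference = 0.23 × (mean effect to week 6) + 0.77 × (mean effect after week 6).

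**Step 3. Illustrations**

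The documents give no trajectory, so these patterns are assumptions. The effect at week 6 is set to 1.

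| Assumed arm difference | 6-month mean as share of week-6 effect |
|---|---|
| 1 to day 42, then 0 | 42/182 = 23% |
| 1 to day 42, then 0.5 | (42 + 70)/182 = 62% |
| Linear rise to 1 at day 42, then 1 | (21 + 140)/182 = 88% |
| Constant at 1 throughout | 182/182 = 100% |
| Linear rise to 1 at day 42, linear to 1.5 at day 84, then 1.5 | (21 + 52.5 + 147)/182 = 121% |

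A constant difference makes the two quantities equal. It is sufficient but not necessary: a linear rise to day 42 followed by 1.15 gives (21 + 161)/182 = 100%.

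**Step 4. If CPAP data end sooner than 6 months**

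| Last day of data | Nights after week 6 | Nights after week 7 |
|---|---|---|
| 84 (week 12) | 42/84 = 50% | 35/84 = 42% |
| 105 (week 15) | 63/105 = 60% | 56/105 = 53% |
| 182 (6 months, as written) | 140/182 = 77% | 133/182 = 73% |

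At every end date, at least half of the nights fall after the time point in the hypothesis.

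**The case against.** The simplest defence is that 6 months is a slip for 6 weeks. It may be. If so, the numerical consequence disappears and a wording correction remains, which would still have to decide between adherence at week 6 and a mean over six weeks. But the period is written twice, and nothing in the text shows which was meant.

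A second defence is that CPAP data arrive passively ("Weekly Updates on Critical Adherence Monitoring Data Variables") with no stated end, so six months of data could exist. That is fair, and the point here is not that collection is impossible. Available data would still not make a 6-month mean test a 6-week hypothesis. Conversely, if data stop at week 12, later nights no longer dominate, as step 4 shows; but then the plan as written is not being followed.

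Third, the seven weeks of coaching are an expected frequency, not a defined end of intervention. Chat, data-triggered outreach and web access to adherence data have no stated end, and Table 1.0 puts the first peer-coach call in week 2. The 73% is therefore approximate, and nights after week 7 are not strictly nights without intervention. The 77% after week 6 does not depend on this.

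Fourth, any replacement window brings its own averaging. Under the linear-rise pattern, a mean over days 29-42 is about 35/42 = 83% of the week-6 value, and a mean over days 1-42 is 50%. No window is best under every pattern. This stands, and it is a reason to name the window and word the aim to match it.

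Finally, a 6-week estimate could be derived from the secondary interaction model. That is true, but the plan neither specifies it nor makes it primary.

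**Conclusion.** The concern holds. Aim 1 and the primary hypothesis specify 6 weeks, the primary model specifies 6 months, and nothing in the plan reconciles them. No CPAP analysis as written directly estimates adherence at 6 weeks.

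If the plan is followed literally, 77% of the nights entering the primary comparison come after the time point being tested. In the illustrations, the resulting estimate runs from 23% to 121% of the week-6 effect, so the longer window cannot be called conservative. These figures rest on a 182-day window from randomization, complete nightly data and assumed trajectories; they show that the discrepancy can be large and go either way, and do not predict its value. The contradiction itself rests on no assumption. It must be corrected, because it concerns what the primary analysis estimates.

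**What to change.** Before any outcome data are seen, reconcile the two periods and make one arm contrast primary.

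- **If 6 weeks is intended**, as Aim 1 and the hypothesis both say, replace the 6-month period in both sentences with a stated window counted from randomization. One option is a closing window ending at week 6 (days 29-42 is an example), with the aim stating that this is what at 6 weeks means. The other is days 1-42, with Aim 1 and the hypothesis reworded as mean adherence over the first six weeks. Analyse later nights as a secondary question of maintenance.
- **If 6 months is intended**, reword Aim 1 and the hypothesis, and state that CPAP data are collected for 6 months.
- **In either case**, define day zero and give the CPAP data cut-off.

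The cost is a few sentences. A 6-week window needs no additional data; a 6-month window requires collection to that point to be written into the protocol.

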Participant completes the following steps independently [see Appendix A for randomization workflow]:

- 1) Portal Registration
- 2) E-Consent Signature
- 3) Self-reported confirmation of eligibility survey

Participant and Research Coordinator via First Phone Call:

- 4) Confirmation of Eligibility (i.e. self-report survey and research team confirmation)
- 5) Medical History
- 6) Demographic Information collected by research team
- 7) Self-Report Oxygen Prescriptions and Adherence (if applicable)
- 8) Participants data-steward provides access to CPAP data
- 9) Wireless Data Access confirmed by research team
- 10) ~30-days of baseline CPAP data uploaded to portal (collected retroactively)
- 11) Baseline Survey Package

Once these steps have been completed the research team will be notified both within the study portal and by email; the notification will indicate that the participant is now ready to be randomized.

Envelopes have been made ahead of time and should not be opened ahead of time. The randomization envelope reveals, with equal odds, either the Proactive Care Arm or the Reactive Care Arm. The coordinator will immediately mark the individual as such in their participant profile, within the study portal. See Appendix C for both Respiratory Therapist and Peer Coaching scripts.

Proactive Care Arm

- 1) The Proactive Care arm of the study is considered the study intervention. If an individual is randomized to the proactive care arm they have access to: Weekly Dyadic Peer Coaching
- 2) Respiratory Therapist Dyadic Coaching
- 3) A seven-module online curriculum covering topics on COPD, OSA and Overlap Syndrome
- 4) Web-based access to adherence data
- 5) Proactive, dyadic, web-based and telephone support from Peer Coaches to congratulate progress and troubleshoot difficult weeks

Reactive Care Arm

- 1) Web-based access to adherence data
- 2) Reactive, dyadic, telephone-based support

Figure 1 below shows a simplified, visual representation of the study design.

[figure not shown]

Figure 1.0 Study Design, Study Surveys and Peer Support

Study Activities

Table 1.0 O₂VERLAP Study Activities

Week

Activity	Who's involved?	1	2	3	4	5	6	7	8-15
Portal Registration	Patient	X							
E-Consent	Patient	X							
Self-report eligibility survey	Patient	X							
Confirmation of Eligibility survey	Coordinator	X							
Medical History	Coordinator	X							
Demographic Survey	Coordinator	X							

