C.O.P.D Information Line peer coaches are available to participants Monday through Friday, from 9:00am to 6:00pm ET. If a participant calls the Information Line and does not reach an associate, calls are returned within 24 hours of the last business day. The C.O.P.D. Information Line Peer Coach's availability to the proactive and reactive care arms of the study is the same. There proactive care arm however, will have additional avenues of communicating with the C.O.P.D. Information Line peer coaches (i.e. the chat feature of the study portal) and will also have scheduled calls to check-in with the peer coaches on a weekly basis.

The scheduled calls between proactive care arm participants and peer coaches will be used to discuss progress in the curriculum and weekly CPAP adherence monitoring data. Peer coaches will also reach out to a proactive care arm participant if the portal indicates that they need help, this can happen in a number of ways, such as:

- A participant may indicate in a specific module lesson that they would like to speak with a peer coach
- A participant may choose to send a message to the peer coaches using the chat function within the study portal
- The participant's adherence data may show that they improved their adherence significantly and should be congratulated
- The participant's adherence monitoring data may show that they are adhering at a level below their baseline

Individuals in the reactive care arm will be given the C.O.P.D. Information Line number and told that they can call it whenever they wish, however, they will not have scheduled calls with peer coaches and their study portal data will not trigger peer coaches to call them when they are having a particularly successful or difficult week.

Individuals in the proactive care arm will likely speak with Information Line Coaches at least once a week during their initial seven weeks in the study. Peer-coaches will also be very important in providing emotional and social support to all participants.

Additionally, there will also be certified Respiratory Therapists who are providing peer coaching from the perspective of a caregiver.

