All study participants will have a call with a Respiratory Therapist (RT) peer coach at the beginning of the study, to discuss their 30-days of baseline remote adherence monitoring data. This will be an opportunity for the participant to reflect on their current habits and set personal goals for improvement. The RT coaches will ask questions to help determine how well their current Sleep Apnea Mask is fitting them; this will also be an initial step to troubleshoot individually with participants and provide possible solutions to obvious adherence barriers.

The coaches will all be guided and trained on proper interactions with participants, however, no peer-coaches should ever provide the participant with clinical advice. If a coach believes that a participant needs clinical advice they will advise them to contact their preferred healthcare provider.

Quality Tracking and Improvement of Communication Between Peer Coaches and Participants

If a peer coach feels that a participant needs clinical support, should discuss a topic further with a healthcare provider or needs to seek emergency help they will suggest the participant do so. It is required that the peer coaches document any scenario where this occurs. The study portal has a communications tracking survey which peer coaches are required to fill out after each interaction with a participant. The survey captures the mode of communication, date, time and asks the peer coach to provide information on the topics discussed. The survey specifically asks if the coach advised a participant to speak with a healthcare provider or seek medical attention.

The completion of the coach's communication tracking form triggers a similar form in the participants activity list. This provides the participant a chance to rate their interaction on a scale of one to ten, one being not satisfied at all and ten being completely satisfied. It also asks that the participant share what was discussed. If a participant rates their interaction to be a seven or lower we will consider this insufficient and it will immediately trigger the peer coaches to reach back out to the participant. The peer coaches should acknowledge that the participant may not have been satisfied and ask if they can help further. The peer coaches will additionally ask how their communication can be improved upon to apply to future communications.

Data Analysis and Data Monitoring

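### No analysis has a term for coach, so if coaches differ in effect the standard error of the arm comparison is too small for conclusions beyond the coaches used

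*Combined protocol and SAP*

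**What the plan says.** **Analysis.** Under Study Primary Aim (section III, Data Analysis and Data Monitoring), daily CPAP adherence goes into a random effects model. "A random intercept will be included in the model to account for the repeated measures of CPAP" is completed by "adherence over 6 months within each patient", so the random effect belongs to the patient. (The six-month horizon in that sentence is a separate matter.) The secondary analysis of adherence adds at most a random slope. Study Secondary Aims uses ANCOVA, multivariable linear regression and a random effects model for correlation within the participant, and Study Tertiary Aim refers back to these. Coach appears nowhere as a random effect, a fixed effect, a cluster for robust variance or a sensitivity analysis. The overarching approach states that "all analyses will be performed using two- sided tests with alpha=0.05".

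**Delivery.** The opening summary says that participants "will additionally have weekly check ins with their coaches". The Peer Coaches section gives the proactive arm "scheduled calls to check-in with the peer coaches on a weekly basis", plus outreach triggered by portal data. Reactive participants get the Information Line number but no scheduled peer-coach calls. Every participant has one initial RT call; Table 1.0 lists the later RT calls for the proactive arm only.

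**Coach numbers and records.** The number of coaches and their caseloads are not stated, and the readable text has no rule assigning participants to coaches. Coaches must complete a tracking survey after each interaction: "The survey captures the mode of communication, date, time and asks the peer coach to provide information on the topics discussed". Coach identity is not among the fields listed.

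**The concern.** Coaching is a main component of the intervention, and part of its content varies by coach. Coaches offer advice from their own experience, and the Appendix C script has them insert a personal statement. The plan also expects contacts to vary in quality, since each is rated and a low rating triggers a further call.

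Participants who share a coach share whatever that coach adds or fails to add. Because sustained contact is scheduled in one arm only, the design is close to partially nested: grouped by coach in the proactive arm and nearly ungrouped in the reactive arm. A model whose only random effects are for the participant treats coached participants as independent of one another. If coaches differ, the mean of the proactive arm carries a component of variance that the model does not see. The confidence interval for the arm effect is then too narrow, and the test rejects more often than the stated 5%. A favourable result could partly reflect who happened to be coaching.

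**Working it through.** **The plan's own figure.** Under Number of subjects: "The goal is to recruit 330 participants into the study to result in analyzable data of 300 participants (assumes ~10% attrition"). 300 × 1.10 = 330, which is the stated target. Dividing instead gives 300 / 0.90 = 333.3, so 334; and 330 × 0.90 = 297. The target is reproduced within rounding of the attrition allowance, and no design effect enters it. No effect size, SD or power is stated, so there is no power figure to check.

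**Inputs from the documents.**
- Two-sided alpha of 0.05.
- 1:1 allocation of individuals ("The randomization envelope reveals, with equal odds, either the Proactive Care Arm or the Reactive Care Arm"), so 300 / 2 = 150 analysed per arm.

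**Inputs assumed, because the documents give none.**
- K coaches with equal caseloads, K = 3, 5, 10 or 20.
- Coach ICC of 0, 0.01, 0.02 or 0.05.
- No clustering in the reactive arm.

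**Formulas.** With m = 150 / K participants per coach:
- design effect in the proactive arm: DE = 1 + (m − 1) × ICC
- true SE / model SE: R = √((1 + DE) / 2)
- actual alpha = 2 × (1 − Φ(1.96 / R))

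Worked case, K = 5 and ICC = 0.05: m = 30; DE = 1 + 29 × 0.05 = 2.45; R = √(3.45 / 2) = 1.313; 1.96 / 1.313 = 1.493; alpha = 0.136.

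| Coaches | ICC | DE | R | Actual alpha |
|---|---|---|---|---|
| any | 0 | 1.00 | 1.00 | 0.050 |
| 20 | 0.01 | 1.065 | 1.016 | 0.054 |
| 20 | 0.05 | 1.325 | 1.078 | 0.069 |
| 10 | 0.01 | 1.14 | 1.034 | 0.058 |
| 10 | 0.05 | 1.70 | 1.162 | 0.092 |
| 5 | 0.01 | 1.29 | 1.070 | 0.067 |
| 5 | 0.02 | 1.58 | 1.136 | 0.084 |
| 5 | 0.05 | 2.45 | 1.313 | 0.136 |
| 3 | 0.01 | 1.49 | 1.116 | 0.079 |
| 3 | 0.02 | 1.98 | 1.221 | 0.108 |
| 3 | 0.05 | 3.45 | 1.492 | 0.189 |

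**Does rotation help?** With fixed coaches, and total variance set to 1, the variance of the proactive mean is ICC/K + (1 − ICC)/150. If every participant is instead spread evenly over all coaches, the same average of K coach effects enters the mean, so the variance is the same. Simulation of participant-level means (20,000 trials per setting) compared one fixed coach with seven calls to randomly drawn coaches:

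| Coaches, ICC | Fixed coach | Rota |
|---|---|---|
| 20, 0.01 | 0.055 | 0.051 |
| 5, 0.01 | 0.069 | 0.067 |
| 5, 0.05 | 0.137 | 0.139 |
| 3, 0.05 | 0.194 | 0.196 |

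The differences are small and go both ways, and the fixed-coach column agrees with the formula.

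**Can a coach random effect be estimated?** Under a rota most of the coach variance shifts the whole arm and leaves little trace within it. In 1,000 simulated trials per setting at ICC 0.05 under a rota, a coach effect weighted by contact share was estimated as zero in about half of the trials (51% with 5 coaches, 53% with 3).

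**The case against.** **The size rests on assumed inputs.** This stands. A reader might infer from the role of the Information Line that a small pool of coaches delivers the intervention. The documents do not say so. With 20 coaches and an ICC of 0.01, the alpha of 0.054 is negligible.

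**One coach per participant is not established.** This also stands. The Appendix C scripts speak of a coach for the day and of a team that checks messages, which suits a shared line. An assignment rule may sit in the Appendix A workflow, whose figure is not reproduced, so the plan cannot be faulted for lacking one. A reader might infer that a rota removes the problem, but the calculation shows that it does not.

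**The inflation is conditional.** Participants are randomised individually. If the programme has no effect through any coach, coaches cannot differ in effect and clustering does not inflate the test. If inference is restricted to the coaches actually used, the planned standard error is close to adequate, and that is a defensible target. However, section IV says that the trial should show whether the programme is a helpful tool for the overlap syndrome community, which reaches beyond one team.

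**The ICC may be low.** Coaches are trained and scripted, and the curriculum and adherence data are delivered online. This is a fair reason to expect a small ICC, but not to assume zero.

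**The reactive arm is not free of shared staff.** Correct: it has one RT call and access to the same line. The contrast in scheduled contact remains large.

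**Coach identity may already be recoverable.** Possibly. Coaches complete the form in a portal with an audit trail, and Appendix D describes user names tied to individuals. The absence of coach identity from the listed fields does not prove a data gap.

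**Conclusion.** The concern holds in conditional form. Every planned analysis accounts for correlation within the participant only, while sustained scheduled coach contact is essentially confined to the proactive arm. If coaches differ in effect, and the conclusion is meant for the programme beyond these coaches, the standard error of the arm effect is too small: by about 2% with 20 coaches and ICC 0.01 (1 − 1/1.016), and by 33% with 3 coaches and ICC 0.05 (1 − 1/1.492). The corresponding alphas run from about 0.054 to 0.189, against 0.05 when the ICC is zero.

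These figures assume 150 analysed per arm, equal caseloads and an unclustered reactive arm. The documents cannot place the trial within the range, and they do not support a claim that its type I error is in fact inflated. That justifies a pre-specified sensitivity analysis, not a new primary model.

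**What to change.** 1. State the number of coaches (peer and RT) and how participants are assigned to them.
2. Record coach identity for every contact on the mandatory communications tracking form, or confirm that it will be taken from the portal audit trail.
3. Keep the main models. Beside each main arm contrast under the primary, secondary and tertiary aims, pre-specify a sensitivity analysis with a coach random effect in the proactive arm only, and with small-sample degrees of freedom. If coaches rotate, use a multiple-membership form weighted by each coach's share of the participant's contacts. Report the estimated coach variance.
4. Because that variance is poorly estimated with few coaches or under a rota, also report the arm-effect confidence interval inflated at assumed ICCs of, for example, 0, 0.01, 0.02 and 0.05, using the observed caseloads.
5. State that a zero estimate of coach variance will not be read as proof of robustness. Under a rota the coach model then collapses to the main model and has tested nothing.

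The cost is at most one field on an existing form and a few sentences in the analysis section. The downside is wider intervals in the sensitivity analysis and an imprecise coach variance. Coach identity should be secured before contacts accumulate, since it may not be recoverable later.
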